8.5.3 ANALYSIS OF THE SECONDARY ENDPOINT(S)

For secondary outcomes, continuous data will be reported as means with SDs and between-arm differences in means will be calculated using Student's t-tests or non-parametric statistics. To account for repeated measures, secondary analysis will be conducted to calculate within (baseline, 6 months, 12 months) and between arm-differences to evaluate changes.

We will compare baseline adjusted self-reported mean HbA1c at 12 months between those in the intervention versus control arms. This will be done using linear regression to estimate the effect of the intervention on HbA1c.. The same Bayesian model as the primary analysis will be used. We will adjust for by sex and gender.

From the process evaluation, we will report metrics of user engagement by # of interested topics chosen by the participant, type of specific topics, proactive use of chatbot, response rate (%) to messages that query participants with a question or prompt requiring a SMS response, and proportion (%) of participant clicks on resource and educational links. Furthermore, qualitative observations made during the one-on-one interviews and surveys administered during the process evaluation will be analyzed using thematic analysis strategies guided by HAPA and the TAM, identifying key themes that demonstrate important contextual influences and practices related to the implementation and evaluation of the e-Health technologies in actual contexts of health care delivery. The findings of the qualitative data will be used to develop statements of the relationships between (a) key contextual factors (e.g., perceived needs, outcome expectancies, self-efficacy), (b) the mechanisms by which they affect the implementation of the e-Health interventions, and (c) the impact on the outcomes of the KiT intervention themselves (in Realist Evaluation these statements are referred to as “Context-Mechanism-Outcome Configurations” (43).

For the Coincidence Analysis, we will create individual case constructions for all trial participants that will triangulate intervention engagement data by intervention component with outcome data, using pathways informed by the semi-structured interviews. Where required, variable values will be converted to have categorical properties according to the definitions and criteria developed by the research team. CNA package in R will be used for data analysis.

The descriptive cost analysis of the aggregate and direct medical costs associated with the KiT intervention will be conducted from the perspective of the Ontario MOHLTC and adopted over a life of the intervention period. We will assume a 1.5% discount rate for costs and consequences going beyond 1 year as per the Canadian Agency for Drugs and Technology in Health (CADTH) guidelines for economic evaluations (44). All costs will be reported in 2023 Canadian dollars using the Bank of Canada Consumer Price Index calculator to adjust for inflation to a given base year (45). We will utilize a bottom-up approach when tallying the healthcare resource utilization costs for individuals over the study duration. Healthcare resource utilization costs will consist of the ED visits, hospitalizations, and physician visits, and diabetes drug and devices claims, as well as other relevant services as decided with the study stakeholders during follow-up. Costs related to hospitalizations and emergency room visits will be estimated using the resource intensity weight (RIW) methodology, whereby the cost is the product of the RIW associated with a particular case and the average cost per weighted case for Ontario and Québec (44). Furthermore, we will simulate the scaling of the program and its impact on the program and health system costs.

Analyses for the preliminary safety and performance KiT LLM chatbot testing will include descriptively describing whether the LLM Evaluator acts more conservatively than human raters when scoring answers, and if the answers generated by KiT LLM are acceptable based on the graded criteria (see section 9). After the trial is completed, CDTx (UHN) will analyze conversation logs between participants and KiT LLM to derive effective engagement with the bot. This will include analyzing the conversation between participants and KiT LLM (eg, duration, breadth, and depth of bot usage). The performance of the LLM Evaluator will also be assessed by evaluating conversations flagged and any potentially sensitive conversations missed. This evaluation will provide insights into how KiT LLM was used in a real-world setting and opportunities to improve its performance over time.

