From pediatric to adult diabetes care: The incidence of type 1 diabetes (T1D) in Canada is amongst the highest in the world (1). In 2012, there were 6,676 children under 18 years of age living with T1D in Ontario alone(11). As these children enter emerging adulthood, they face challenges that complicate the transition to adult diabetes care. One single-centre study in the United States found that 34% of T1D patients transitioning to adult programs reported a gap of more than 6 months in establishing adult care(12). Using data from Ontario, we showed that almost half of emerging adults with T1D had a gap exceeding 12 months between their last pediatric appointment and the time they saw their eventual adult diabetes care physician(13). This may be due to a number of recognized barriers for emerging adults, including making a connection with the new adult team, difficulties communicating with the new clinic regarding scheduling appointments, and lack of perceived value in the clinic visit(14). Many emerging adults arrive at adult clinics feeling inadequately prepared for transition and are often not counselled on topics relevant to their specific needs. Feeling unprepared for adult care has been associated with an increased risk of having a gap of more than 6 months between pediatric and adult care(15). Further, we have shown that the struggles that transitioning T1D patients experience in taking on multiple new responsibilities and adult providers' lack of appreciation of these struggles are key barriers to successful transition. We have also found that upon the transfer to adult care there was often no sharing of a formal medical summary(16). These studies have identified the need for improved transition preparation, care coordination, and communication between pediatric and adult providers(15). We have shown that there is

variability in transition practices across Ontario pediatric diabetes centres(13). There is an urgent need to develop a system-level innovative approach to help emerging adults remain engaged in their care during this vulnerable period.

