3 OBJECTIVES AND ENDPOINTS

The **primary objective** of this study is to compare the effectiveness of a text message-based T1D transition intervention that will personalize transition education and support, as an adjunct to usual T1D transition care versus usual transition care alone on a patient-reported outcome measures (PROM) called the Self-Efficacy for Diabetes Management (SEDM) scale, measured at baseline, 6 months, and 12 months after enrollment in the study.

The **secondary objectives** of this study are to evaluate the impact of this text-messaging based intervention on:

- other patient reported experiences and outcomes (PREMs/PROMs) including the READY tool, a transition readiness assessment for emerging adults with diabetes diagnosed in youth; and the Barriers to Diabetes Adherence in Adolescence (BDA) questionnaire Stigma Subscale for assessing perceived stigma
- self-reported time between final pediatric diabetes visit and first adult diabetes visit
- self-reported and/or lab reported A1c at baseline and at 12 months after enrollment to study (depending on data availability)
- diabetes-related ED visits (measured using self-reported, medical chart and health administrative data)
- diabetes-related hospitalizations (measured using self-reported, medical chart and health administrative data)
- Aggregate and direct medical costs associated with the intervention and its implementation study data and administrative data)
- Exploring how the KiT large language model (LLM) chatbot is used in a real-world setting for more natural conversations and opportunities for us to improve its performance over time. The LLM chatbot is not a learning model and will only utilize existing resources gathered for the KiT study.

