9 STATISTICAL CONSIDERATIONS

8.2 STATISTICAL HYPOTHESES

- **Primary Endpoint(s):** Diabetes self-efficacy measured by SEDM at baseline, 6 and 12 months after baseline. We hypothesize that the intervention will improve engagement with support content and improve self-management of diabetes among the intervention group compared to control group at 12 months compared to baseline.
- **Secondary Endpoint(s):** transition readiness measured by the READDY tool; perceived stigma measured by the Barriers to Diabetes Adherence (BDA) stigma subscale, and time from final pediatric to first adult diabetes appointment; HbA1c; diabetes-related ED visits and hospitalizations at 12 months. We hypothesize that the intervention, may improve transition readiness and improve glycemic management, decrease the time from last pediatric to first adult diabetes appointment, and decrease the frequency of diabetes-related ED visits and hospitalizations in the intervention group compared to the control group at 12 months compared to baseline.
- **Exploratory Endpoint(s):**
 - Within the embedded process evaluation, we will investigate the pragmatic nature of this trial and study whether making real-time adjustments will improve user interaction and experience will increase user uptake and satisfaction. We will also identify the different paths of engagement (i.e., combinations of KiT components) that produce a positive effect on trial outcomes.
 - We will measure the cost of implementing this intervention to inform the feasibility of scaling this intervention.
 - We will explore if socioeconomic status as measured by material deprivation quintile is related to the use, engagement and effectiveness of the KiT intervention on diabetes self-

efficacy and/or the readiness to transition to adult diabetes care, and/or barriers to diabetes adherence stigma subscale.

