8.4 POPULATIONS FOR ANALYSES

The conventional frequentist analyses are often interpreted in a dichotomous matter, based on the p-value chosen as threshold for 'statistical significance' and 'no evidence of effect' is confounded with 'evidence of no effect'. A Bayesian analysis will be conducted to provide the probability of any benefit or harm. An intention-to-treat analysis will be conducted by blinded analysts. We will evaluate the extent of missing data to determine if values are missing at random or not and will consider imputation to account for missing values.

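### Section 8.5.3's difference-in-means rule does not suit the pediatric-to-adult care gap, because a participant with no adult visit by month 12 has no gap to average

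*Protocol*

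**What the plan says.** Section 3 of the protocol lists "self-reported time between final pediatric diabetes visit and first adult diabetes visit" among the secondary objectives. Section 8.2 repeats it among the secondary endpoints ("and time from final pediatric to first adult diabetes appointment"). The hypothesis in 8.2 is hedged with 'may' but has a direction: the intervention may "decrease the time from last pediatric to first adult diabetes appointment".

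Section 8.5.3 gives HbA1c its own model and does not mention the gap. For continuous secondary outcomes in general it says that "continuous data will be reported as means with SDs and between-arm differences in means will be calculated using" Student's "t-tests or non-parametric statistics". Section 8.4 promises an intention-to-treat analysis and says missing data will be examined to "determine if values are missing at random or not and will consider imputation to account for missing values".

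On timing, sections 4.1 and 5.1 place enrolment within 3–4 months of the planned final pediatric visit or transfer, or of the 18th birthday. Section 5.4 (step 11) puts the last questionnaires 12 months after enrolment.

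Section 2.2 gives two background rates. In Ontario data, "almost half of emerging adults with T1D had a gap exceeding 12 months". At a single US centre, "34% of T1D patients transitioning to adult programs reported a gap of more than 6 months".

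**The concern.** A gap is a duration with a start and an end. If the end has not happened when self-report stops, all that is known is that the gap exceeds the time observed. A mean cannot use that information, so a between-arm difference in means has to rest on those who did attend. Whether a participant attends in time is itself something the intervention is meant to change. The two groups of attenders are therefore no longer the randomised groups, and the comparison is not the intention-to-treat one promised in 8.4.

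Two things are at stake. First, most of an effect on attendance can vanish from the comparison, because those who would show it are left out of the control mean. Second, the result can point the wrong way: extra people brought in late lengthen the attender mean in the intervention arm although nobody was slower.

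**Working it through.** The protocol states no power or sample size for this endpoint, so there is no figure to reproduce.

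**1. Observation window.** Window w = 12 months minus the lead time from enrolment to the final pediatric visit. A lead of 4 months gives 12 − 4 = 8; a lead of 0 gives 12. On the birthday route, a final visit that comes later leaves less than 8.

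**2. Share of gaps unobserved (illustration).** Assume exponential gaps at the section 2.2 rates, so S(w) = S(t₀)^(w/t₀).

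- Ontario, 'almost half' over 12 months read as 45–50%: at w = 12, 45–50%; at w = 8, 0.45^(8/12) = 59% and 0.50^(8/12) = 63%.
- US, 34% over 6 months: at w = 12, 0.34² = 12%; at w = 8, 0.34^(8/6) = 24%.

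**3. One worked power case.** Section 8.3 allows for 20% loss from 117 per arm: 117 × 0.8 ≈ 94 evaluable. Take Ontario at 50%, w = 12 and an attendance hazard ratio of 1.5 (assumed).

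- λ₀ = ln 2 / 12 = 0.0578; λ₁ = 1.5 × λ₀ = 0.0866 per month.
- Attending by w: 1 − 0.5 = 50% (47 of 94) and 1 − 0.5^1.5 = 65% (61 of 94).
- Attender mean = 1/λ − w·e^(−λw)/(1 − e^(−λw)): control 17.31 − 12.00 = 5.31; KiT 11.54 − 6.56 = 4.98. The difference is 0.33 months, against a true difference in means of 17.31 − 11.54 = 5.8.
- Attender variance = 1/λ² − w²·e^(−λw)/(1 − e^(−λw))²: 11.7 and 11.4. SE = √(11.7/47 + 11.4/61) = 0.66. t-test power ≈ Φ(0.33/0.66 − 1.96) ≈ 7%.
- Log-rank with 47 + 61 = 108 events: Φ(√108/2 × ln 1.5 − 1.96) = Φ(0.15) ≈ 56%.

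**4. Simulation** (4,000 trials per setting, 94 per arm, two-sided 5%, hazard ratio 1.5, exponential gaps). With no effect, the t-test rejected in 4.2–4.9% and log-rank in 4.6–5.3%.

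| Setting | t-test, attenders only | Log-rank |
|---|---|---|
| Ontario 50%, w = 8 / 12 | 6.0% / 7.3% | 45.7% / 54.7% |
| Ontario 48%, w = 8 / 12 | 6.2% / 8.8% | 47.2% / 58.0% |
| US, w = 8 / 12 | 21.9% / 41.3% | 71.1% / 76.0% |

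A repeat of the Ontario 50% setting gave 6–8% against 45–56%. A rank test with non-attenders ranked last had about 43–53% (Ontario 50%) and 64–66% (US).

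**5. Direction.** Suppose nobody is slowed and a further share of the KiT arm attends in the last third of the window. Ontario 50%, w = 12, 15 points added: attendance rises from 50% to 65%, while the attender mean goes from 5.31 to (0.50 × 5.31 + 0.15 × 10)/0.65 = 6.39 months.

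| Added late attenders | KiT mean longer | Significantly longer (t-test) | Log-rank in wrong direction |
|---|---|---|---|
| 10–15% of arm | 87–95% of trials | 20–38% | 4–15% |
| 5% of arm | 72–75% | 8–10% | 27–30% |

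**6. Where log-rank gains little or loses.** With almost all gaps observed (US, Weibull shape 2, w = 12, 1.3% unobserved), power is 68% for the t-test against 78%. If 45% of both arms never attend and KiT only speeds up attenders (mean 3 versus 4 months), the t-test has 13–20% against 7–10% for log-rank.

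**The case against.** The protocol nowhere says that non-attenders are dropped. A reader might infer a planned attenders-only analysis, but 8.5.3 does not name the endpoint and 8.4 commits to intention to treat. This stands, so the point is not that the exclusion is stated. It is that the one stated rule yields no number for a non-attender.

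The non-parametric option in 8.5.3 is not empty. A rank test with non-attenders ranked last recovers most of the power (working, step 4). But the sentence ties that option to differences in means and gives non-attenders no rank. The imputation to be considered under 8.4 does not cover gaps that are absent because they are long.

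It is tempting to say that at least 42–47 of 94 controls (0.45–0.50 × 94) must be unobserved. The documents do not support that bound. The Ontario rate in 2.2 measures time to the eventual adult diabetes physician, which can be later than the first adult visit, and both rates come from populations other than consenting trial participants enrolled before transfer.

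Nor do the documents show that the result will reverse. That depends on the added attenders arriving late.

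Section 4.1 plans administrative and self-reported data for at least 12 months, and 8.5.3 counts physician visits for costing, but section 3 defines this endpoint as self-reported.

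An analysis plan not shown here could add the detail. However, the protocol already fixes a general rule, and it is a poor fit. The endpoint's weight is modest: it is missing from the synopsis's secondary endpoints in 3.1, and its hypothesis is hedged.

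**Conclusion.** The concern holds for this one secondary endpoint. As written, the only rule that reaches the care gap can be computed for attenders alone, unless a ranking or censoring convention is added that the protocol does not state.

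That some gaps will be unobserved follows from the follow-up schedule. How many is uncertain: 12–24% (US rate) to 45–63% (Ontario rate) if those rates applied and gaps were exponential, and close to none under the most favourable shape tried. The power figures (about 6–9% against 45–58%, Ontario; 22–41% against 71–76%, US) further assume 94 evaluable per arm and a hazard ratio of 1.5. They are illustrations, not predictions. A wrong-direction result is possible if the intervention mainly adds late attenders; log-rank has no advantage if it only speeds up people who attend anyway. The change should be made before outcomes are analysed. The primary SEDM analysis is unaffected.

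**What to change.** In 8.5.3, take this endpoint out of the difference-in-means rule and state that:

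- all randomised participants with a known final pediatric visit are analysed by time to event from that visit;
- those without an adult visit are censored at their last completed questionnaire;
- results are shown as Kaplan-Meier curves by arm, with a site-stratified log-rank test or Cox model (at minimum, a rank test with non-attenders ranked last);
- the proportion with an adult visit is reported by arm, so that a change in who attends can be told from a change in speed;
- the number with no final pediatric visit by month 12, who have no start time, is reported by arm;
- any mean among attenders is descriptive only.

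The cost is a few sentences and routine code. It needs self-reported visit dates or months. The endpoint already presupposes these, but the survey items are not shown, so their availability is an assumption.

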1 PROTOCOL SUMMARY

1.1 SCHEMA

Prior to Enrollment (21 month Recruitment Period)

Total 234: Screen potential participants by inclusion and exclusion criteria, obtain informed consent, Assign Study ID number

Randomize on REDCap (done by local coordinator)

KiT intervention arm (117 participants)

Control arm (117 participants)

Baseline

Local coordinator: securely transfer Memotext Study ID, Randomization arm and phone number of newly randomized participant. Memotext to activate enrollment by sending start-text to participants in **both arms**

Local coordinators: Collect HbA1c lab-reported value no later than 6 months prior to enrolment date, emergency department and hospitalization data, and OHIP/RAMQ numbers to link to admin data

Memotext: sends SMS of baseline questionnaires as URLs that linkout to REDCap for: KiT demographic Survey ,READDY, BDA Stigma Subscale, and SEDM **to both arms**

Intervention Start

Memotext: based on READDY tool responses, sends SMS of T1D-related questions, support, and management **to only intervention arm for 12 months. Both groups receive usual medical care during intervention period.**

6-Month

Follow-up assessments: Memotext sends SMS of 6-month questionnaires as URLs that linkout to REDCap: KiT Survey, READDY, BDA Stigma Subscale, SEDM **to both arms.** Interim Process Evaluation with intervention arm

12-Month

KiT intervention modification: based on results of process evaluation; adjustments or modification to KiT algorithm will be made to improve message and content delivery, and improve user engagement and satisfaction

Final Follow-up assessments: Memotext sends SMS of 12-month questionnaires as URLs that linkout to REDCap: KiT Survey,READDY, BDA Stigma Subscale, and SEDM **to both arms.** Process Evaluation, Health System utilization and Cost of implementation analysis performed at end of intervention.

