evaluate the impact of this text message-based intervention on the following, compared to the usual transition care alone: 
 • Transition readiness • perceived stigma of living with T1D • self-reported time between final pediatric diabetes visit and first adult diabetes visit • self-reported and/or lab reported A1c at baseline and at 12 months after enrollment to study (depending on data availability) • diabetes related ED visits • diabetes related hospitalization • Cost of implementation • Explore how the KiT LLM chatbot is used in a real-world setting for more natural conversations and opportunities for us to improve its performance over time. The LLM chatbot is not a learning model and will only utilize 	
 • transition readiness measured by the READDY tool at baseline, 6 and 12 months; READDY is a transition readiness assessment for emerging adults with diabetes diagnosed in youth. The READDY tool assesses diabetes-related knowledge or skill items by querying respondents on 42 total items split into 5 domains: knowledge, navigation, health behaviors, and insulin pump skills. Respondents answer on a Likert scale from “yes, I can do this” to “Haven’t thought about it”; confidence level is evaluated in each domain • the Barriers to Diabetes Adherence in Adolescence questionnaire (BDA) Stigma Subscale; in our study, stigma will be defined as an affirmative response to at least one of three key items on this subscale • A1c collected at baseline and 12 months after enrollment to study will be self-reported and/or lab-reported (depending on data availability) • Diabetes related ED visits, hospitalizations, will be measured for the 12 months prior to and 12 months during the intervention using self-reported, medical chart, and health administrative data from ICES. • Costs of implementation • LLM chatbot data 	
 • The READDY tool has been validated during its development by examining its correlation with existing validated transition readiness tools such as TRAQ(40); the READDY tool was favored by the KiT subcommittee that included a patient partner. The KiT subcommittee felt that compared to other transition readiness scales specific to diabetes, the READDY tool was specific and relevant to what is being evaluated and it is patient-reported • the Barriers to Diabetes Adherence in Adolescence questionnaire was developed to measure psychosocial barriers to adherence in adolescents with T1D; the stigma subscale has previously shown to be useful in research and clinical settings(41) • HbA1c: From long-term follow up of the landmark Diabetes Control and Complications Trial (DCCT) participants, early metabolic control has a lasting legacy. Individuals randomized

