- 1) From Medical Charts: first and last name, telephone number and email in order for local research coordinator to establish contact with eligible participants during recruitment phase, either in clinic or virtually via telephone or email. Participant's HbA1c value within 6 months prior to enrollment, mailing address including 6-digit postal code will also be obtained from their medical chart. The full mailing address is needed to send study information letters and/or baseline, 6 month or 12 month reminder letters (if preferred by participant versus email communication). Additionally, the full 6-digit postal code is needed for ICES verification during linkage of participant OHIP number to administrative data sets, and for socioeconomic analysis using the deprivation index , which requires the use of 6-digit postal codes. Diabetes related ED visits, and hospitalizations will be measured for the 12 months prior to enrolment to evaluate the impact of this text message-based intervention, compared to the usual transition care alone. Only local research coordinators will access information from patient medical charts after obtaining local REB approval and institutional approval for this study. PHI data from participant medical charts will be stored on the enrollment log (encrypted and on password-protected computer).
- 2) Provincial Health Card Number: All participant consent forms will indicate that we are collecting OHIP (in Ontario) and RAMQ (in Quebec) numbers in order to perform linkage to provincial administrative data . We will be recording and storing the OHIP and/or RAMQ numbers on a log separate from all other data collection documents and will not enter this information into REDCap or the KiT intervention algorithm, or the enrollment log or Master Linking log. Memotext will not have access to participants' OHIP and/or RAMQ number. Upon study data collection completion, all participating sites will upload their participant OHIP/RAMQ number to a secure file portal in order to enable administrative data linkage via ICES in Ontario and Med-Echo and Régie de l'assurance maladie du Québec (RAMQ) databases in Quebec. To enable

verification of provincial health card number for linkage to administrative datasets, ICES and RAMQ will receive participant full first and last name, Study ID number, OHIP or RAMQ number, full date of birth, sex and full 6-digit postal code.

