Memotext protects personal information by security safeguards appropriate to the sensitivity of information. They are committed to keeping personal information secure, and have appropriate technical, administrative, and physical procedures in place to protect personal information against loss or theft, as well as authorized access, disclosure, copying, use, modification, disposal or destruction. In addition, methods of protection and safeguards include, but are not limited to, locked filing cabinets, restricted access to offices, security clearances, need-to-know access and technological measures including the use of passwords, encryption and firewalls.

Data collection for secondary outcomes measured using administrative data: We will securely link patients' health card number to provincial administrative databases housed at ICES in Ontario and Med-Echo and Régie de l'assurance maladie du Québec (RAMQ) databases in Quebec. The study investigators will be permitted to access de-sensitized information only for analysis (i.e., any information that can directly identify a person like health card number or name will be removed or replaced with a code that is not known to the study investigators). We will measure all diabetes-related hospitalizations, emergency department visits, and HbA1c results (Ontario only from the Ontario Lab Information System (OLIS)), in the 12 months prior to enrollment in the study and for 12 months after enrollment. In Ontario we will also collect information on hospitalizations for DKA or hypoglycemia from the Canadian Institute of Health Information (CIHI) discharge abstract database (DAD) and emergency department visits for hyper/hypoglycemia will be ascertained using the National Ambulatory Clinic Reporting System (NACRs). In Quebec we will measure hospitalizations from Med-Echo (hospitalizations) and RAMQ databases (physician billings from hospitalizations) and emergency department visits for hypo/hyperglycemia will be identified from the RAMQ databases. A data sharing agreement will be in place for this transfer, between ICES and SickKids.

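### Section 8.5.3 ties the 12-month HbA1c comparison to self-report, against the protocol's own endpoint definition and with no stated role for the Ontario lab values it links

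*Protocol*

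**What the plan says.** The analysis section (8.5.3) fixes the HbA1c comparison in one sentence: "We will compare baseline adjusted self-reported mean HbA1c at 12 months between those in the intervention versus control arms". It adds that "The same Bayesian model as the primary analysis will be used", so the 95% probability threshold in 8.5.2 presumably carries over.

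The endpoint table in section 3 is wider: "A1c collected at baseline and 12 months after enrollment to study will be self-reported and/or lab-reported (depending on data availability". The list of secondary objectives in section 3 says the same, and section 7.1 also allows either source.

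Lab values are planned from two places:

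- **Before enrolment, from the site.** The schema (1.1) tells local coordinators "Collect HbA1c lab-reported value no later than 6 months prior to enrolment date". Section 10.1.6.1 lists, among chart data, "Participant's HbA1c value within 6 months prior to enrollment".
- **By linkage, Ontario only.** Section 10.1.6.1 includes "HbA1c results (Ontario only from the Ontario Lab Information System (OLIS)), in the 12 months prior to enrollment in the study", and the same sentence extends this to 12 months after enrolment. Section 8.1 repeats that administrative HbA1c is for Ontario only.

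Section 4.2 states that participants know their allocation.

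**The concern.** A definition that admits two sources has been narrowed, in the section that fixes the model, to the weaker one. A self-reported HbA1c depends on what the participant remembers, how recently a test was done, and how they wish to present it. All three could differ by arm here. Participants know their allocation, KiT teaches about A1c and targets (Appendix, Table 2), and its sample dialogue offers a reminder to have A1c bloodwork done (Appendix, Table 3). Controls get no such content or reminders (6.1.1).

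The primary outcome, SEDM, is itself unblinded self-report. A measured HbA1c would be useful corroboration; a self-reported one shares the same weakness. The linked Ontario results are less exposed to this, yet 8.5.3 gives them no stated role in the HbA1c model.

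**Working it through.** **1. The sections side by side**

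| Place | HbA1c source | Time |
|---|---|---|
| Section 3, objectives and endpoint table | self-report and/or lab | baseline, 12 months |
| 7.1 | self-report or lab | baseline, 12 months |
| 8.1 and 10.1.6.1, linkage | lab, Ontario only | 12 months before to 12 months after enrolment |
| 1.1 and 10.1.6.1, site data | lab or chart value | within 6 months before enrolment |
| 8.5.3, HbA1c model | self-report only | 12 months; baseline source not named |

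Section 8.5.3 conflicts with the first two rows and does not use the third.

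**2. How many participants linked lab data could reach**

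Section 8.3 forecasts about 120 Ontario and 90 Quebec participants after losses: 120 / (120 + 90) = 0.571. Before losses the share is the same: 152 / (152 + 114) = 0.571. This is a ceiling, because it assumes that every Ontario participant has a usable result.

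**3. The baseline**

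Section 8.5.3 does not say whether the covariate is the self-reported or the lab value. The questionnaires include glycemia items at each time point (6.1.1), so self-report at both times is a possible reading. If the sources did differ, randomisation would still make the adjusted arm contrast unbiased; only precision would suffer.

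**4. Illustration of bias (assumed values)**

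The protocol gives no HbA1c SD, reliability, correlation or power figure; its only power statement concerns SEDM. Inputs are:

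- n per arm = 117 × 0.8 = 93.6, from section 8.3;
- assumed SD 1.3 to 1.7 and assumed baseline correlation 0.6;
- assumed reporting difference of 0.2 points in favour of KiT, with no true effect;
- a flat prior, so that a 95% posterior threshold acts like a one-sided 5% test.

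SE = SD × √(1 − 0.6²) × √(2/93.6) = SD × 0.8 × 0.1462, which is 0.152 for SD 1.3 and 0.199 for SD 1.7.

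Chance of a false benefit = 1 − Φ(1.645 − 0.2/SE):

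- SD 1.3: 1 − Φ(0.329) = 0.37
- SD 1.7: 1 − Φ(0.639) = 0.26

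Without a reporting difference it is 0.05.

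If lab values replaced self-report at the 57% ceiling, equally in both arms, the 0.2 would shrink to 0.2 × (1 − 0.571) = 0.086. The chance would then be 1 − Φ(1.081) = 0.14 (SD 1.3) or 1 − Φ(1.214) = 0.11 (SD 1.7). Mixing sources dilutes the problem but does not remove it.

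**5. Illustration of random error (assumed values)**

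Relative to lab values at both times, a self-reported outcome of reliability r with a lab baseline correlated ρ multiplies the SE by √[(1/r − ρ²)/(1 − ρ²)]:

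- r = 0.95, ρ = 0.5: √(0.8026/0.75) = 1.03
- r = 0.70, ρ = 0.7: √(0.9386/0.51) = 1.36

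This is a loss of precision of 3% to 36%, without bias.

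**The case against.** The best defence is that self-report is the only 12-month source described for both provinces, and one uniform source has merit. Lab availability after randomisation may depend on arm, because KiT can prompt bloodwork and controls get no reminders. It may also be selective: section 2.2 reports that almost half of Ontario emerging adults had a gap of over 12 months before reaching adult care. A lab-first rule therefore brings its own bias risk. This stands. It is why availability must be shown by arm, and why source should not be a covariate in the main model.

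It may also be said that windows and source rules belong in the statistical analysis plan. That would answer silence, but 8.5.3 names a source, and it conflicts with the endpoint definition.

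Several stronger readings are tempting and are not supported:

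- **That a self-reported outcome will be adjusted for a lab baseline.** The text leaves the baseline source open, and a mismatch would not bias the comparison.
- **That the linked lab values are discarded altogether.** 8.5.3 opens with a general plan for continuous secondary outcomes, which does not exclude them. What is missing is a role in the HbA1c model.
- **That lab values could replace self-report throughout.** No month-12 chart extraction is planned, nor any systematic Quebec lab source.
- **That HbA1c is the only objective check on the primary result.** ED visits and hospitalisations are also taken from administrative data.

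**Conclusion.** The point holds as an inconsistency with a practical consequence. Section 8.5.3 restricts the HbA1c comparison to unblinded self-report, contrary to section 3 and section 7.1, and leaves planned Ontario lab results without a stated part in that model.

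The size of any differential reporting cannot be established from the documents. The rise from 5% to about 26–37% and the 3–36% loss of precision rest wholly on assumed SDs, correlations, reliabilities and a 0.2-point shift. The only figure from the protocol itself is the coverage ceiling of about 57%. The matter is worth correcting before outcome data are seen, so that the source is not chosen on results. It concerns one secondary endpoint and does not touch the SEDM analysis.

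**What to change.** Amend 8.5.3 to agree with section 3:

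1. Define 12-month HbA1c as the linked lab value within a stated window ending at month 12 where one exists, and self-report otherwise. Record the source for each participant. The window has to look back, because linkage stops 12 months after enrolment.
2. Name one baseline source: the pre-enrolment lab or chart value collected at all sites.
3. Add a lab-only analysis in Ontario participants using the linked data.
4. Report lab availability by arm.
5. Do not adjust for source in the main model, since it arises after randomisation and KiT reminders may affect it. Do not count on month-12 chart values or Quebec lab results.

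**Cost.** This is mainly wording, since the linkage is already planned. The team should confirm that self-reported and linked values can be combined per participant under the data-sharing agreements; section 10.1.6.1 already sends the Study ID for linkage. The downside is that lab coverage is at most about 57%, probably lower, and may differ by arm. The combined outcome therefore keeps some self-report, and the Ontario analysis is smaller and may be selective.
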